4.4.2 Secondary assessments based on questionnaires and visual acuity

This will involve intention-to-treat comparisons among all randomised participants of the effects of allocation to fenofibrate versus placebo during the scheduled treatment period on:

- 4.4.2.1 Visual function (based on the Visual Function Questionnaire [VFQ]-25 questionnaire)
- 4.4.2.2 Quality of life (based on the EuroQol- 5 Dimension [EQ-5D] questionnaire)
- 4.4.2.3 Visual acuity (based on visual acuity on LogMar or Snellen chart score collected during NHS retinal screening)

4.4.3 Health economic assessments

Health economic assessments will be conducted to help guide the appropriate use of fenofibrate by health care providers. The detailed analysis plan for health economic assessments will be described in a separate document.

4.5 Tertiary efficacy assessments

4.5.1 Tertiary assessments based on clinical events

This will involve intention-to-treat analyses among all randomised participants of the effects of allocation to fenofibrate versus placebo during the scheduled treatment period on time to the first occurrence of:

- 4.5.1.1 The composite of any major cardiovascular event (defined as myocardial infarction, stroke, coronary or peripheral revascularisation).
- 4.5.1.2 The composite of any non-traumatic lower limb amputation (defined as minor amputation [distal to the ankle] or major amputation [through or proximal to the ankle]).

4.5.2 Tertiary assessments based on biochemistry

Intention-to-treat analyses of the effects of allocation to fenofibrate versus placebo will be conducted on the following measures:

- 4.5.2.1 Urine albumin: creatinine ratio

4.6 Clinical safety assessments

SAEs and reasons for stopping study treatment will be captured in the study database to be used for safety assessments. The safety assessments will include intention-to-treat analyses among all randomised participants of the effects of allocation to fenofibrate versus placebo during the scheduled treatment period (with due allowance in their interpretation for multiple comparisons) on:

- 4.6.1.1 Serious adverse events by Medical Dictionary for Regulatory Activities (MedDRA, version 14.0) System Organ Class classification;

^c progression from R'X' (baseline) to >R'X' or from M'X' (baseline) to >M'X' in either eye

^d M2 grading in the NHS Scotland grading scheme

4.6.1.2 Discontinuation of study treatment, overall and by various causes

4.7 Other laboratory assessments

Intention-to-treat analyses of the effects of allocation to fenofibrate versus placebo will be conducted on the following measures:

4.7.1.1 eGFR^e

4.7.1.2 Lipids (total cholesterol, non-HDL cholesterol, HDL cholesterol, triglycerides)

4.7.1.3 HbA1c

Invitation to routine NHS retinal screening is determined by the most recent retinal screening results (and has also been affected by the COVID-19 pandemic). The mean (standard error) number of retinal screening visits per participant will be calculated for each treatment arm.

5 Analysis sets for efficacy and safety analyses

For all outcomes, analyses will compare the outcome from randomisation to the end of the scheduled treatment period (see Section 7.5) among all those participants who are allocated at randomisation to receive fenofibrate versus all those allocated to receive matching placebo (i.e. “intention-to-treat” analyses).^{3,4} Analyses of binary outcomes will be based on the first occurrence of the specified outcome. *Per protocol* analyses will not be conducted because of the potential for bias in such non-randomised assessments.

In accordance with the protocol, primary, secondary and tertiary outcomes will not be adjudicated with the exception of any medical eye procedures, any adverse event reports of vitreous haemorrhage and any adverse event reports of macular oedema. Such events will be adjudicated by clinicians blinded to the study treatment assignment (see Section 6). For those events that are subject to adjudication, analyses will include confirmed and unrefuted events (excluding any events adjudged to be related to a cause other than diabetic retinopathy).

For eye outcome events, the number of people experiencing the outcome (in one or both eyes) will be compared between the treatment groups (rather than the total number of eyes affected).

6 Ascertainment and adjudication of study endpoints

6.1 Ascertainment of information

Unless consent to follow-up is withdrawn, follow-up information is to be collected from all study participants, irrespective of whether or not they continue to receive study treatment. If a participant becomes unwilling or unable to complete follow up study assessments by telephone then study clinic staff will review the available medical records and complete the necessary Follow-up form on the clinic IT system. Information will also be collected from linkage to NHS Scotland healthcare systems and registries. Where retinopathy and maculopathy gradings of retinal images contribute to pre-specified outcomes, the grading results generated by the NHS Scotland Diabetic Eye Screening

^e Based on calculations using serum creatinine collected by data linkage and the CKD EPI formula:

$eGFR = 141 \times \min(\text{Scr}/k, 1)^\alpha \times \max(\text{Scr}/k, 1)^{-1.209} \times 0.993^{\text{Age}} \times 1.018$ [if female] $\times 1.159$ [if African American]

where:

Scr is serum creatinine in $\mu\text{mol}/\text{L}$; k is 61.9 for females and 79.6 for males; α is -0.329 for females and -0.411 for males; min indicates the minimum of Scr/k or 1; max indicates the maximum of Scr/k or 1

program will be used. However, it is also intended to use image analysis software at a later time to repeat these analyses.

6.2 Adjudication

Adjudicators will follow the standardised procedures in accordance with the pre-specified endpoint definitions and adjudication procedures as described in the Adjudication Charter (LENS Adjudication Charter and Outcome Definitions EDMS #6781). Only one blinded adjudicator will execute the adjudication procedure for each event.

7 Statistical methodology for efficacy and safety analyses

7.1 Methods of analysis

All participants randomised to receive fenofibrate will be compared with all participants randomised to placebo, irrespective of whether they received all, some or none of their allocated treatment (i.e. intention-to-treat [ITT] analyses).^{3,4}

For the time-to-event analyses, survival analytic methods will be used to evaluate the time to the first event during the entire study period. Cox proportional hazards regression analyses, adjusted for baseline covariates used in minimised randomisation, will be used to estimate the hazard ratios, 95% confidence intervals and corresponding p-values, comparing all participants allocated active fenofibrate with all those allocated placebo.³ The proportional hazards assumption will be assessed through examination of the Schoenfeld residuals. The Kaplan-Meier estimate will also be plotted for the time to the primary outcome (with its associated log-rank p-value). When separately assessing individual elements of composite outcomes, a participant may contribute to more than one assessment if they have events of more than one type (e.g. significant retinopathy followed by laser treatment). All p-values will be 2-sided. For each of the events listed as additional safety outcomes (Section 4.6), the number of randomised participants with at least 1 event will be compared using standard tests for differences in proportions.

For continuous measures collected only at the screening visit, or which may plausibly be affected by fenofibrate treatment during the active run-in (namely visual function, quality of life, eGFR, lipids [total cholesterol, non-HDL cholesterol, HDL cholesterol, triglycerides], HbA1c, urine albumin: creatinine ratio), the screening visit value will be considered to represent the 'baseline' value to which any post-randomisation values are compared. For continuous measures not collected at the screening visit but identified in pre-randomisation NHS linkage data (namely visual acuity), the latest value within 18 months prior to randomisation will be considered to represent the 'baseline' value.

Any continuous outcomes that display substantial positive skew will be analysed on the log scale. For quality of life (Section 4.4.2.2), index values will be derived from EQ-5D-5L questionnaire data using a UK-based value set. Visual acuity (Section 4.4.2.3) will be recorded using the LogMAR or Snellen chart score. The main analysis of visual acuity will be based on the eye with best acuity at baseline, and analysis of the eye with worse acuity will be conducted as a sensitivity analysis. Where the baseline visual acuity is the same in both eyes, the right eye shall be chosen for the main analysis and the left eye for the sensitivity analysis. Analyses of visual function will be based on LogMAR values, with conversion of Snellen chart score to LogMAR values where required^f.

Visual function (Section 4.4.2.1) and quality of life (Section 4.4.2.2) are collected at baseline, at approximately 2 years and at the end of the trial as part of scheduled study assessments. By contrast, biochemical measurements (Sections 4.5.2.1 and 4.7) and visual acuity (Section 4.4.2.3) are collected at baseline and then collected at multiple times during follow-up as part of routine NHS clinical care. For all of these outcomes with baseline and repeated follow-up values, linear mixed

^f LogMAR value = $\log_{10}(\text{Snellen denominator} / \text{Snellen numerator})$; it is recognised that conversion from Snellen chart score to LogMAR value is imperfect but it is considered adequate for comparison of fenofibrate vs. placebo

model repeated measures (MMRM) analyses will be conducted to estimate the mean values by treatment allocation at each follow-up time point, as well as a trial-averaged difference in mean follow-up levels between the randomised treatment groups. For visual function and quality of life, the relevant follow-up time points will be 2 years and the end of the trial but, for biochemical measurements and visual acuity, the follow-up time points will be the midpoint of each year of follow-up (any individuals with >1 value in a given 1-year post-randomisation window of time will have those values averaged prior to the MMRM analysis). These MMRM models will adjust for the baseline value of the measure of interest as well as the baseline minimisation criteria and will assume an unstructured covariance matrix.

7.2 Multiplicity adjustments

Assuming that the trial runs to its planned completion, the primary assessment at the final analysis will be made first and deemed statistically significant if its two-sided p-value is <0.05.

For the secondary and tertiary assessments, multiple testing will not formally be taken into account. However, given the number of such analyses, due allowance will be made in their interpretation, taking into account the nature of events (including timing, duration and severity) and evidence from other studies.^{3,4}

7.3 Subgroup analyses and tests for heterogeneity

The secondary assessments (see Section 4.4.1.1) include intention-to-treat analyses among all randomised participants of the effects of allocation to fenofibrate versus placebo during the scheduled treatment period on the primary outcome in sub-categories of patient based on categories of data collected at baseline. Tests for heterogeneity of the proportional effect observed in subgroups will be used to determine whether the proportional effects in specific subcategories are clearly different from the overall effect.^{2,3} (Note that for the subgroups that can be sensibly ordered [age, renal function and HbA1c] this test for heterogeneity is equivalent to a test for trend because each of the subgroups is to be split into only two categories [see Section 4.4.1.1].)

When many different subgroups are considered, chance alone may lead to there being no apparent effect in some subgroups considered in isolation, even when the effect of treatment really is about the same as is observed overall. In such circumstances, “lack of direct evidence of benefit” is not good “evidence of lack of benefit”, and clearly significant overall results would provide strong indirect evidence of benefit in subgroups where the results, considered in isolation, are not conventionally significant (or, even, perhaps, slightly adverse).³⁻⁵ Hence, unless the proportional effect in some specific subcategory is clearly different from that observed overall, the effect in that subcategory is likely to be best estimated indirectly by applying the proportional effect observed among all patients in the trial to the absolute risk of the event observed among control patients in that category.⁵

7.4 Handling of missing and incomplete data

The study protocol and procedures have been designed to minimise loss to follow-up.⁶ For any binary outcome event where the precise date of occurrence is unknown, the midpoint of the plausible range will be assumed (e.g. the middle of the month if only the month and year are reported). For subgroup analyses of the effects of fenofibrate on such events, patients with missing baseline values for that subgroup will be excluded from the subgroup-specific results but included in the overall total (with the result just among those with missing baseline data for each subgroup explicitly reported if the ‘missing’ category proves to be a non-trivial subset). Note that for analyses of the continuous measurements recorded at multiple follow-up time points, the MMRM models take account of missing data by assuming that such data can be predicted from the correlations seen between the non-missing values for other individuals, together with the other covariates in the model (i.e., the model assumes that data are ‘missing at random’).

7.5 Censoring schema for time-to-event endpoints

For all intention-to-treat analyses, participants who do not have the outcome under investigation will be censored at the end of the scheduled treatment period, which will be defined as the earliest of date of the final follow-up visit, death, or full consent withdrawal. For participants for whom information on these 3 criteria is missing, the censoring date will be set as the date when reliable information on both vital status and the occurrence/absence of the primary outcome was last reliably recorded (e.g. by completion of follow-up visit or access to relevant healthcare records).

8 Guidelines for early stopping or modification of the trial

Unblinded interim analyses will be reviewed regularly by the DMC, and will be conducted and presented by a statistician not involved in the day-to-day management of the trial. Upon review of such data, the DMC will advise the Steering Committee if, in their view, the randomised comparisons have provided both (a) proof beyond reasonable doubt that for all patients, or for some specific types, fenofibrate therapy is clearly indicated or contra-indicated; and (b) evidence that might reasonably be expected to influence materially the clinical management of many patients. The Steering Committee can then decide whether to end or modify the trial or to seek additional data, and this decision will be communicated in writing to the Chief Investigator after each Steering Committee meeting.

Appropriate criteria of proof beyond reasonable doubt cannot be specified precisely, but the DMC will work on the principle that a difference of at least 3 standard errors in an interim analysis of a major outcome event may be needed to justify halting, or modifying, a study before the planned completed recruitment. This criterion has the practical advantage that the exact number of interim analyses would be of little importance, and so no fixed schedule is proposed³.

9 References

1. Cholesterol Treatment Trialists C, Baigent C, Blackwell L, et al. Efficacy and safety of more intensive lowering of LDL cholesterol: a meta-analysis of data from 170,000 participants in 26 randomised trials. *Lancet* 2010; **376**(9753): 1670-81.
6. Fleming TR. Addressing missing data in clinical trials. *Ann Intern Med* 2011; **154**(2): 113-7.

10 Appendix A: Details of randomisation algorithm

The minimised randomisation algorithm allocates participants to the placebo arm or the active arm. The participant is allocated to the treatment arm with the lower minimisation score, with a probability of 0.9 (i.e. this occurs for 90% of randomisations). For the other 10% of randomisations, or in the event of a tie (i.e. minimisation scores are equal), treatment is allocated randomly with a probability of 0.5.

The minimisation score is calculated based on the following categories:

- Sex: male; female
- Age at randomisation visit: <30; $\geq 30 < 50$; $\geq 50 < 70$; ≥ 70 years
- Type of Diabetes: Type 1, Type 2, Other
- eGFR from Randomisation assessment: <60; ≥ 60 mL/min/1.73m²
- HbA1c from Randomisation assessment: <64; ≥ 64 mmol/mol; unknown
- Statin therapy: Yes; No
- Most recent macula result: consider both eyes and use the worst eye's macula result as the category (in the list below, 'i' is the best result and 'iii' is the worst result)
 - i. No result available
 - ii. No maculopathy
 - iii. Observable diabetic maculopathy
- Most recent retina results: consider both eyes and use the worst eye's retina result as the category (in the list below, 'i' is the best result and 'iv' is the worst result)
 - i. Other retinopathy (this includes 'not adequately visualised' and 'other result provided')
 - ii. No retinopathy
 - iii. BDR – Mild
 - iv. BDR – Observable

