#### 3.2 OUTCOMES

##### 3.2.1 Primary outcome

The primary outcome is the composite of progression from observable DR to referable DR, or any of retinal laser therapy, vitrectomy or intra-vitreal injection of medication due to DR. Referable DR is defined according to the Scottish DES grading as R3 or R4 or M2 in at least one eye on the DES grading scheme (see Table 1).

For those participants in whom the composite primary outcome is reported (whether via data linkage or questionnaire), LCC research nurses will review their electronic health records periodically to determine any therapy, i.e. retinal laser, vitrectomy or intra-vitreal injection, which was provided. While most primary outcomes are expected to come from routine retinal imaging, any findings of referable DR recorded during clinical examination (e.g. by an ophthalmologist) will also be included as an outcome.

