## 6 STATISTICS AND DATA ANALYSIS

### 6.1 SAMPLE SIZE CALCULATION

Availability of prospective NHS Scotland DES data allowed progression rates for DR to be calculated directly from the target population in which LENS will be conducted. Data in Table 6 indicate DR progression rates (limited to patients with at least 3 years' follow-up and a baseline result prior to 2009). If it is assumed that participants will be recruited from among the various grades with observable DR in proportion to their prevalence, the progression rate from observable to 'referable' DR would be approximately 29% over 4 years. On that basis, 1060 participants would yield approximately 222 events over an average follow-up of 4 years, providing 85% power to detect a 33% reduction in progression (allowing for 15% drop-out) at alpha = 0.05. We aim to randomise at least 1060 participants.

As described in LENS' inclusion criteria, patients with R1 DR will need to have bilateral rather than unilateral R1 given that progression rates to referable DR are 2.4X and 3.7X higher in type 1 DM and type 2 DM respectively with bilateral R1 compared with unilateral R1. Inclusion of patients with unilateral R1 would substantially reduce event rates.

The LENS composite primary outcome consists of progression of observable DR to referable DR, or any of retinal laser therapy, vitrectomy or intra-vitreal injection of medication due to DR. While DR progression is likely to dominate in terms of numbers of events, this composite outcome has been selected to avoid missing any unexpected rapid progression of DR which requires intervention before the next DES screening visit.

**Table 6.** Progression rates of DR in Scotland (baseline data pre-2009)

	Progression to referable retinopathy or maculopathy over 3 years*			
Baseline grading	M2	R3	R4	M2 or R3 or R4
Type 1 DM (n=14,354)				
R0 M0 (n=7,202)	131 (1.8%)	204 (2.8%)	12 (0.2%)	347 (4.8%)
R1 (one eye) M0 (n=2,480)	170 (6.9%)	21 (0.9%)	24 (1.0%)	215 (8.7%)
R1 (both eyes) M0** (n=4,016)	622 (15.5%)	121 (3.0%)	102 (2.5%)	845 (21.0%)
R2 or M1** (n=656)	237 (36.1%)	64 (9.8%)	48 (7.3%)	349 (53.2%)
Type 2 DM (126,639)				
R0 M0 (n=92,543)	942 (1.0%)	73 (0.1%)	82 (0.1%)	1,097 (1.2%)
R1 (one eye) M0 (n=20,147)	822 (4.1%)	62 (0.3%)	45 (0.2%)	929 (4.6%)
R1 (both eyes) M0** (n=11,978)	1,663 (13.9%)	264 (2.2%)	128 (1.1%)	2,055 (17.2%)
R2 or M1** (n=1,971)	530 (26.9%)	184 (9.3%)	60 (3.0%)	774 (39.3%)

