3.1 Study design

LENS is a randomised placebo-controlled trial investigating the effects of prolonged treatment with the PPAR alpha agonist, fenofibrate on the progression of diabetic eye disease. At least 1,060 participants with observable diabetic retinopathy or maculopathy will be randomised (using a minimisation algorithm, see Appendix A: Details of randomisation algorithm) between oral fenofibrate 145mg or placebo tablets. Study treatment is taken once daily in the context of normal renal function, or as one tablet every second day in the context of reduced renal function. Follow up is scheduled to continue until at least 222 primary outcome events have occurred and median follow up (counting from the date of randomisation of the median participant) is at least 4 years.

The trial is designed to be streamlined. Most data for pre-specified efficacy outcomes is obtained by linkage to NHS Scotland records. Only the Screening and Randomisation assessments occur in person, and all subsequent assessments occur by telephone or by reference to medical records. Study treatment is mailed to participants' homes. After the initial Screening visit is conducted and safety blood tests are performed, eligible individuals (who are approved to enter the run-in by the local investigator) are provided with active fenofibrate 145mg tablets to be taken (daily with normal renal function, one tablet every second day with reduced renal function) for approximately 8 weeks. They are then asked to return to the study clinic for a Randomisation assessment. If they remain eligible based on information collected at this assessment and further safety blood tests, and are willing to continue, participants are randomly allocated to fenofibrate 145mg tablets or placebo.

No research blood or urine samples are taken from randomised participants. Linkage to NHS Scotland data-sets is performed to obtain results for HbA1c, renal function (serum creatinine, eGFR, urine albumin, urine albumin creatinine ratio) and other assays (e.g. lipids) that have been collected as part of routine care.

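### SAP 7.5 carries event-free participants to a telephone or record-based final visit even if their eyes were last assessed much earlier, and no planned analysis tests what that does to image-detected outcomes

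*SAP*

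**What the plan says.** **Censoring.** SAP 7.5 ends event-free time at the close of the scheduled treatment period, "defined as the earliest of date of the final follow-up visit, death, or full consent withdrawal". Only when information on all three is missing does it fall back on "the date when reliable information on both vital status and the occurrence/absence of the primary outcome was last reliably recorded". It gives a completed follow-up visit, or access to healthcare records, as examples of what satisfies that fallback.

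**What a follow-up visit is.** SAP 3.1 says that after randomisation "all subsequent assessments occur by telephone or by reference to medical records". Protocol 4.7.3 lists the questionnaire content: it asks about eye procedures but cannot yield a retinal grade.

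**Where the outcome comes from.** Protocol 3.2.1: "While most primary outcomes are expected to come from routine retinal imaging", with referable disease found at clinical examination also counted. The images are those of the routine NHS screening programme (DES), every 6-12 months (Protocol Table 2). The trial does not schedule them.

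**What is planned about imaging.** SAP 4.7 notes that screening invitations depend on the latest result and were affected by COVID-19. It plans the mean number of screening visits per participant by arm. SAP 7.4 covers unknown event dates, missing subgroup values and missing continuous data, but not gaps in imaging.

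**The concern.** Referable retinopathy, any grade progression (SAP 4.4.1.3) and M2 (SAP 4.4.1.4) are known to be absent only up to the last gradable image or eye examination. Suppose someone's last usable image was at month 12 but they answer the telephone at year 4. Under SAP 7.5 they count as free of referable disease for 4 years, unless clinic or procedure records show otherwise.

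Two things are at stake:

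- **Absolute risk.** The Kaplan-Meier curve for the primary outcome (SAP 7.1) would read too low. SAP 7.3 applies the overall proportional effect to the absolute risk seen in control patients, so the level matters as well as the ratio.
- **Hazard ratio.** If loss of imaging differed between arms, the arm with more loss would appear to have fewer events.

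The mean number of visits per arm would not settle either question. It does not show how long before censoring an eye was last assessed, and it varies with grade-driven recall.

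**Working it through.** **1. The plan's own figures.** Protocol 6.1 plans 1,060 randomised, about 222 events and a 4-year average follow-up. It describes the calculation as "providing 85% power to detect a 33% reduction in progression (allowing for 15% drop-out) at alpha = 0.05", and puts control progression at "approximately 29% over 4 years". SAP 7.1 makes the test two-sided: "All p-values will be 2-sided".

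- Events needed (Schoenfeld): 4 × (1.960 + 1.036)² / (ln 0.67)² = 224, against 222 stated.
- Power with 222 events: Φ(√(222/4) × |ln 0.67| − 1.960) = 0.847, against 85% stated.
- Expected events: 0.85 × 530 × [0.29 + (1 − 0.71^0.67)] = 450.5 × (0.290 + 0.205) = 223.

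The design figures reproduce, so there is no sample-size error here.

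**2. Simulation set-up.** Placebo hazard is −ln(0.71)/4 = 0.0856 per year. Images are yearly with a random starting phase, and an event is dated at the first image after onset. A stated share of each arm stops being imaged at a uniform random time over 4 years, independently of progression. There are 0.6-1 million participants per arm, with the final visit at 4.0 years and a repeat at 4.2 years. **The stopping shares are assumed; the documents give none.**

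**3. Equal loss of imaging, SAP rule.**

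| Stop imaging (each arm) | Placebo 4-year risk (true 29.0%) | HR, true 1.00 | HR, true 0.67 |
|---|---|---|---|
| 0% | 25.8% | about 1.00 | 0.67 |
| 10% | 24.5% | about 1.00 | 0.67 |
| 20% | 23.0% | about 1.00 | 0.67 |

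The fall from 29% to about 26% is detection lag and occurs with full attendance. Only the further fall comes from counting unimaged time.

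**4. Unequal loss.**

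| Stop (fenofibrate / placebo) | True 1.00: SAP rule | True 1.00: last-image Cox | True 0.67: SAP rule | True 0.67: last-image Cox |
|---|---|---|---|---|
| 20% / 10% | 0.94 | 1.01-1.02 | 0.63 | 0.68 |
| 10% / 20% | 1.07 | 0.99 | 0.71-0.72 | 0.66 |
| 13% / 10% | 0.98 | 1.01 | 0.66 | 0.68 |

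With 222 events the standard error of the log hazard ratio is 2/√222 = 0.134.

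- At 20%/10%, two-sided type I error is Φ(−1.960 + 0.49) + Φ(−1.960 − 0.49), about 8%.
- At 10%/20%, power for a true 0.67 falls from 0.847 to about 0.70.

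**5. Could chance produce this?** With 530 per arm, the standard error of 20% minus 10% is √((0.16 + 0.09)/530) = 2.2 points. A 10-point gap is therefore over 4 standard errors. A 3-point gap (13% v 10%) is about 1.5 standard errors, and moves the null log hazard ratio by 0.02, or 0.15 of its standard error.

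**6. Which alternative estimates what?**

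- *Cox censored at the last image* nearly restores the hazard ratio (step 4).
- *Kaplan-Meier censored at the last image* overstates absolute risk. Events are dated at an image while event-free people leave at theirs, so the late risk set empties. A true 29% reads about 31% with the final visit at 4.2 years, and 45% or more with it at 4.0.
- *Interval-censored likelihood ending at the last image* recovers 28.9-29.1%, and hazard ratios of 0.99-1.01 and 0.665-0.674.

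**The case against.** **Other sources fill part of the gap.** Clinical examination findings count, questionnaires ask about eye procedures, staff review records when telephone contact fails (SAP 6.1), and DES and SCI Diabetes linkage repeats every 6-12 months (Protocol 4.6.4). If half of the otherwise unseen events are caught, the 20%/10% scenario gives 0.975 at the null and 0.654 for a true 0.67. This stands, but only in part. In the LENS-eligible rows of Protocol Table 6, M2 accounts for 3,052 of 4,023 progressions (76%). The footnote to Protocol Table 1 says that M2 stopped leading automatically to ophthalmology under a change phased in from 2022.

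**Nothing shows that imaging will differ by arm.** Treatment is double-blind with matching tablets, and the screening service does not know whose images belong to LENS participants (Protocol 4.1). This stands. Recall depends on grade, so an effective drug could alter imaging, but that changes the interval between images more than it ends imaging. In an extreme contrast (12-monthly on fenofibrate, 6-monthly on placebo, nobody stopping), the null hazard ratio reads 0.92 under the SAP rule. Last-image Cox gives 1.04 and the interval-censored analysis 1.00.

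**The 29% is itself from screening data.** It is already image-detected, so treating it as the true onset risk and then adding lag may count the lag twice. This stands as a caution on the 29%-to-26% step.

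A reader might infer three stronger things that the documents do not support:

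- *That the SAP's fallback is already the right standard and need only be applied to everyone.* A completed follow-up visit satisfies it, so it does not require an image.
- *That chance imbalance alone would distort the result materially.* Step 5 shows otherwise.
- *That cost per progression averted would be wrong because it is read from the Kaplan-Meier curve.* Protocol 6.2.2 does not say how that quantity is computed, and SAP 4.4.3 defers economics to a separate plan.

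**Conclusion.** The point holds in a limited form. For image-detected outcomes, SAP 7.5 counts time in which the outcome could not be seen as event-free, apart from events caught by clinic or procedure records. No planned analysis shows how much such time there is or whether it matters.

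- **Equal loss of imaging:** the hazard ratio is unbiased. Absolute risk is understated: beyond the roughly 26% due to lag alone, it falls to 24-25% with 10% stopping and 23% with 20%.
- **Unequal loss:** a 10-point difference moves a null hazard ratio to about 0.94 or 1.07, and a true 0.67 to about 0.63 or 0.72. A chance-sized difference gives about 0.98 at the null.

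It would be wrong to conclude that the primary hazard ratio is biased. That needs differential loss, for which the documents give no evidence. The sizes rest on assumed stopping rates, yearly imaging, a constant hazard and stopping unrelated to progression. Stopping related to progression was not modelled. I rate this a cheap improvement, not a flaw in the primary analysis.

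**What to change.** Keep the primary intention-to-treat Cox analysis and its censoring rule. For the primary outcome and SAP 4.4.1.3 and 4.4.1.4, pre-specify:

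1. **A Cox sensitivity analysis, for the hazard ratio only,** censoring event-free participants at their last gradable DES result or documented eye examination. State this in those words; a reference to the existing fallback would not achieve it.
2. **An interval-censored estimate if absolute risk is reported.** Do not use a Kaplan-Meier curve censored at the last image.
3. **By arm, the time from last gradable eye assessment to censoring,** alongside the planned mean number of screening visits.

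The cost is SAP wording and a little more analysis from dates already obtained by linkage, with no new data collection. Participants with no eye assessment after randomisation contribute no time to the sensitivity analysis, so their number should be given by arm.
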